4.2.3.2.1 Definition of Efficacy Endpoints

In this study clinical response and microbiological response will be evaluated at the EOT and TOC visits. Refer to the following details of definitions for each efficacy response.

4.2.3.2.1.1 Clinical response

Clinical response will be assessed for all subjects based on evaluation by the investigator at the EOT and TOC visits. Based on comparison to baseline clinical signs and symptoms of the subject's infection(s), the investigator will determine the clinical response rating (and record the response on the appropriate eCRF) at each visit as described in [Table 2](#) (for EOT visit) and [Table 3](#) (for TOC visit).

In support of evaluation of efficacy endpoints that include clinical response, the clinical response rating determined by the investigator at each visit will be categorized as "favorable" or "unfavorable". Details regarding determination of the category of clinical response ("favorable" or "unfavorable") in support of relevant study endpoints are provided in the tables describing clinical response as well as Section 8.4.2.

Table 2 Definitions of the Clinical Response Rating at the EOT Visit

Clinical Response ^a	Response Definition
Cure	All pretherapy signs and symptoms ^b of the index infection(s) have resolved (or returned to "preinfection status") AND no additional IV antibiotic therapy is required, AND , for cIAI subjects, no unplanned surgical procedures or percutaneous drainage procedures have been performed.
Improved	All or most pretherapy signs and symptoms ^b of the index infection(s) have improved or resolved (or returned to "preinfection status") AND no additional IV antibiotic therapy is required, AND , for cIAI subjects, no unplanned surgical procedures or percutaneous drainage procedures have been performed.
Failure	No apparent response to IV study therapy in prestudy signs and symptoms ^b of the index infection(s): persistence or progression of most or all pretherapy signs and symptoms.

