Indeterminate	Study data are not available for evaluation of clinical response for any reasons at the EOT visit, including: a) Complication related to underlying medical condition; OR b) Subject was discontinued for any reason before sufficient data had been obtained to permit evaluation for any reason; OR c) Extenuating circumstances preclude classification as "cure", "improved" or "failure" OR d) Death occurred during the study period and the index infection was clearly noncontributory.

^a A favorable clinical response at EOT requires an assessment of "cure" or "improved".
^b Refer to [Table 14](#) in section 7.1.2.6 for a description of disease-specific clinical signs and symptoms.

Table 3 Definitions of the Clinical Response Rating at the TOC Visit

Clinical Response ^a	Response Definition
Cure	All pretherapy signs and symptoms ^b of the index infection(s) have resolved (or returned to "preinfection status") AND no additional IV antibiotic therapy is required, AND , for cIAI subjects, no unplanned surgical procedures or percutaneous drainage procedures have been performed.
Failure	No apparent or insufficient response to IV study therapy in prestudy signs and symptoms of the index infection(s): persistence, progression, or improvement (without full resolution) of all pretherapy signs and symptoms ^b
Indeterminate	Study data are not available for evaluation of efficacy for any reasons, including: a) Complication related to underlying medical condition; OR b) Subject was discontinued for any reason before sufficient data had been obtained to permit evaluation of clinical response; OR c) Extenuating circumstances preclude classification as "cure" or "failure" OR d) Death occurred during the study period and the index infection was clearly noncontributory.

^a A favorable clinical response at TOC visit requires an assessment of "cure".
^b Refer to [Table 14](#) in section 7.1.2.6 for a description of disease-specific clinical signs and symptoms.

4.2.3.2.1.2 Microbiological Response

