8.6.2 Statistical Methods for Efficacy Analyses

Missing values

In the analyses using the ME population, any subject with missing or indeterminate assessments for a specific endpoint (clinical or microbiological response) at any particular visit will be excluded from the assessment of that response at that time point. Exceptions follow:

1. (cIAI only) Subjects with a missing culture in the setting of a favorable clinical response: In such subjects, even in the setting of a missing culture at a particular time point, a favorable microbiological response will be presumed from the clinical response (i.e., "presumptive eradication").
2. Subjects discontinuing IV study therapy due to lack of efficacy (i.e., withdrawals with subsequent non-study antibiotic therapy, subjects requiring therapy beyond 14 days), including death due to index infection:
 - These subjects will be considered to be "failures" with respect to clinical response at the time of discontinuation and all subsequent time points post discontinuation, irrespective of whether the clinical response is listed as "indeterminate".
 - These subjects will be considered to have presumed persistence with respect to microbiological response at the time of discontinuation and all subsequent time points post discontinuation, irrespective of whether the microbiological response is listed as "indeterminate."

In the analyses using the MITT population, missing or indeterminate clinical or microbiological responses will be considered failure.

Proportions of subjects with favorable clinical/microbiological responses

A 95% CI based on the method of Agresti and Coull will be provided for the proportion of subjects with cIAI in the ME population achieving favorable clinical response at the EOT visit. The same analysis will be performed for the proportion of subjects with cUTI in the ME population achieving favorable microbiological response at the EOT visit. The same measures at the TOC visit will also be analyzed in the same manner. Supportive analysis using the MITT population will also be performed.

Table 18 summarizes key efficacy analyses.

Table 18 Analysis Strategy for Key Efficacy Variables

Endpoint/Variable (Description, Time Point)	Primary vs. supportive approach [†]	Statistical Method	Analysis Population	Missing Data Approach
Primary objectives				
Proportion of subjects with cIAI achieving favorable clinical response at the EOT visit	P	Agresti and Coull	ME	Data as observed [‡]

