8.9 Sample Size and Power Calculations

A total of 80 subjects will be enrolled.

For an AE or a specific safety event of interest, if the underlying incidence is 2%, then there is 80% chance that it is observed in at least one subject among the 80 subjects enrolled.

Based on the completed phase II studies (Protocols 003 and 004), it is expected that at least 70% of the enrolled subjects will be included in the ME population. In each of the cIAI and cUTI cohorts, if 40 subjects are enrolled, 28 subjects are included in the ME population and evaluable at the EOT visit, and the 26 subjects achieve favorable response, then the estimated percentage and corresponding 95% CI of subjects achieving favorable response will be 92.9% (76.3%, 99.1%). The estimated percentages and corresponding 95% CIs of subjects achieving favorable response under various assumptions are shown in [Table 19](#).

Table 19 Estimate percentages (95% CIs) of subjects achieving favorable response under various assumptions

Number of subjects		Achieve favorable response	Estimated percentage (95% CI) [†] of subjects achieving favorable response
Enrolled	Included in ME population and evaluable at EOT visit		
30	21	19	90.5 (69.9, 98.6)
		20	95.2 (75.6, 100.0)
40	28	25	89.3 (72.0, 97.1)
		26	92.9 (76.3, 99.1)
		27	96.4 (80.8, 100.0)
50	35	32	91.4 (76.9, 97.8)
		33	94.3 (80.4, 99.4)
		34	97.1 (84.2, 100.0)

[†] Based on the method of Agresti and Coull

The maximum enrollment for each of the cIAI and cUTI cohorts will be limited to 50 subjects to ensure that a single disease cohort will not dominate the study population.

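### For cIAI, an improved or resolved subject at EOT (at TOC, only a fully resolved one) who had an unplanned procedure has no defined clinical rating; choosing Indeterminate removes that subject from the ME estimate

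*Combined protocol and SAP*

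**What the plan says.** Clinical response at EOT is the primary efficacy endpoint for cIAI (Section 3.1), and the ME population is primary for efficacy (Section 8.5.2). The investigator assigns the rating.

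- **EOT, Table 2.** For cIAI, both Cure and Improved carry the condition that "no unplanned surgical procedures or percutaneous drainage procedures have been performed". The condition is not limited to procedures for the index infection. Failure means no apparent response to study therapy, spelled out as "persistence or progression of most or all pretherapy signs and symptoms"; it has no clause on procedures.
- **TOC, Table 3.** There is no Improved rating. Cure carries the same condition. Failure includes improvement that falls short of full resolution, and again has no clause on procedures.
- **Indeterminate, Table 2.** The row opens with "Study data are not available for evaluation of clinical response for any reasons at the EOT visit". Item (a) is a complication of an underlying medical condition. Item (c) begins "Extenuating circumstances preclude classification as" and names the other three ratings.
- **Analysis, Section 8.6.2.** In ME, a subject with an indeterminate response "will be excluded from the assessment of that response at that time point". Exception 2 overrides Indeterminate with failure, but only for "Subjects discontinuing IV study therapy due to lack of efficacy", including death from the index infection. In MITT, "missing or indeterminate clinical or microbiological responses will be considered failure".

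**The concern.** An unplanned procedure rules out the favorable ratings without leading to the unfavorable one. Two investigators facing the same case could reasonably differ: one reads improvement that came only after a drainage as no response to the drug and records Failure; the other records Indeterminate. Neither rating is favorable, so the choice decides only whether the subject stays in the denominator of the ME estimate.

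That matters because the trial is open-label and single-arm with investigator-assigned ratings, so the written definition is the main protection against differences between sites. The plan foresees such procedures: Section 7.1.3.2.2 asks for cultures at any surgical or drainage procedure, and Section 7.1.2.7 collects details of later interventions. Section 8.5.2 has the ME composition documented before database lock. None of these sections says how the case is to be rated.

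**Working it through.** **Step 1. Which subjects have no rating.** Take a cIAI subject with an unplanned procedure who did not discontinue IV therapy for lack of efficacy.

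| Visit and status | Cure | Improved | Failure as worded |
|---|---|---|---|
| EOT, resolved | barred | barred | not met |
| EOT, all or most signs improved | barred | barred | not met |
| TOC, fully resolved | barred | no such rating | not met |
| TOC, improved but not resolved | not met | no such rating | met |

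The gap is the first three rows. Indeterminate (a) or (c) is what remains, although the row's opening words concern unavailable data and here the data exist.

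**Step 2. Reproduce the plan's figure.** Section 8.9 assumes that "28 subjects are included in the ME population and evaluable at the EOT visit", with 26 favorable. Agresti-Coull with z = 1.96, z² = 3.8416:

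p̃ = (x + z²/2)/(n + z²) = (26 + 1.9208)/(28 + 3.8416) = 0.8769

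half-width = z·√[p̃(1 − p̃)/(n + z²)] = 1.96 × √(0.8769 × 0.1231/31.8416) = 0.114

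This gives 92.9% (76.3, 99.1), as stated, with width 99.1 − 76.3 = 22.8 points. All eight rows of Table 19 reproduce in the same way.

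**Step 3. Direction.** With x favorable, excluding rather than failing one subject changes the estimate from x/(n + 1) to x/n. The difference is x/[n(n + 1)], which is positive whenever x > 0. Exclusion can only raise the estimate.

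**Step 4. Size for one assumed case.** The documents give no rate of unplanned procedures, so the count is an assumption. There are two ways to place the case.

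- *Case outside the 28.* The 28 are described as evaluable at EOT, so they already leave out Indeterminates. Excluded: 26/28 = 92.9% (76.3, 99.1). Failure: 26/29 = 89.7% (72.8, 97.2). Difference 26/(28 × 29) = 3.2 points.
- *Case among the two unfavorable subjects.* Excluded: 26/27 = 96.3% (80.2, 100; upper limit capped). Failure: 26/28 = 92.9%. Difference 26/(27 × 28) = 3.4 points.

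Other Table 19 rows, with the case outside the evaluable set:

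| n evaluable | Favorable counts in Table 19 | Shift x/[n(n + 1)], points |
|---|---|---|
| 21 | 19, 20 | 4.1, 4.3 |
| 28 | 25, 26, 27 | 3.1, 3.2, 3.3 |
| 35 | 32, 33, 34 | 2.5, 2.6, 2.7 |

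**Step 5. Range over the assumption, starting from 26/28.** Zero cases: no change. One case: 3.2 or 3.4 points. Two cases: 26/28 − 26/30 = 92.9% − 86.7% = 6.2 points, or 26/26 − 26/28 = 100% − 92.9% = 7.1 points.

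**Step 6. MITT.** Either rating counts as failure there, so the MITT estimate does not move. It does not isolate the effect on ME, because it also contains the subjects who are outside ME or not evaluable: 40 − 28 = 12 in the plan's example.

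**The case against.** The strongest reply is that the text already leans toward Failure. Indeterminate is framed around missing data, and a subject with a complete EOT assessment does not fit it well; improvement only after a rescue procedure can be read as no response to study therapy. The upward shift then needs an investigator to pick the worse-fitting rating. This has force, but Failure as worded also requires persisting or progressing signs, which this subject does not have, and Indeterminate (c) exists for cases that fit none of the other ratings. Item (a) is a further candidate when the procedure arose from another condition.

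The effect is also hypothetical and contained. The documents give no frequency, MITT is unaffected, ME composition is documented before lock, and a supplemental SAP is available. All of this stands and keeps the point small. None of it supplies a rating rule.

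A third reply concerns the remedy. Counting every unplanned procedure as failure would treat unrelated surgery as drug failure and could push the estimate down instead. That also stands: Exception 2 overrides Indeterminate only for lack of efficacy, so the remedy needs a comparable causal limit.

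A reader might infer that an improved subject is unrated at TOC as well. Table 3 does not support this, because improvement without full resolution is already Failure there.

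**Conclusion.** The gap is real, and minor. It covers improved or resolved cIAI subjects at EOT, and only fully resolved ones at TOC, who had an unplanned procedure and did not discontinue IV therapy for lack of efficacy. If such a subject is rated Indeterminate, the ME estimate can only rise: by about 3 points per case at n = 28, and by 4.1 to 4.3 points at n = 21 when the case is added to the denominator. The 95% interval at 26/28 is about 23 points wide.

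These sizes rest on an assumed case. The true number may be zero, and then nothing changes. A reader might infer that the primary cIAI result is biased or that a conclusion is at risk. The documents do not support that: the trial is estimation-only with no decision threshold, and the MITT analysis counts the case as a failure under either rating. The sample-size arithmetic is not in error.

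**What to change.** 1. Add to the Failure rows of Tables 2 and 3: *OR, for cIAI subjects, an unplanned surgical or percutaneous drainage procedure for the index infection has been performed*. Put the same index-infection limit in the Cure and Improved rows, so that the rows match and unrelated surgery neither bars a favorable rating nor counts as failure.
2. Add to Section 8.6.2 or the sSAP a cIAI exception in the form of Exception 2: such subjects are failures for clinical response at that visit and later ones, even if the rating is listed as Indeterminate.
3. Report the number of subjects affected.

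The cost is one clause per table row, one line in the analysis section and a note for those completing the eCRF. Section 7.1.2.7 already collects details of later interventions; the sponsor should confirm that this collection runs through TOC. The downside is that the reported ME rate may be slightly less favorable.

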Persistence ^c	A urine culture taken at the EOT visit ^d grows a uropathogen (at $\geq 10^4$ CFU/mL) found at study entry.
Super infection	An infection-site culture grows a uropathogen (at $\geq 10^5$ CFU/mL) other than a baseline pathogen during the course of IV study therapy OR emergence during IV study therapy of a new pathogen at a distant (non-urine), sterile site along with worsening signs and symptoms of infection.
Indeterminate	
 a) Follow-up urine culture is not available at the EOT visit due to subject death or withdrawal from study; OR b) Microbiological data are incomplete; OR c) Assessment not possible due to protocol violation; OR d) Any other circumstance which makes it impossible to define the microbiological response

^a A microbiological response rating will be determined separately for each pathogen isolated at baseline. If a new/emergent pathogen is identified at this visit which was not identified at baseline, the microbiological response rating will be considered “super infection” for any new/emergent pathogen isolated after initiation of IV study therapy.

^b A favorable overall microbiological response at EOT requires “eradication” of all baseline pathogens.

^c If a subject is discontinued from IV study therapy due to clinical failure (i.e., unfavorable clinical response), but persistence of the admission pathogen is not confirmed by culture results or no culture is obtained at the time of clinical failure, the admission pathogen will be presumed to have persisted.

^d If a culture is not available at EOT, an assessment at this visit can be made from the last available urine culture which was collected after at least 48 hours of IV study therapy.

Table 7 Definitions of the By-Pathogen Microbiological Response for cUTI at the TOC Visit

Microbiological Response ^{a,b}	Response Definition
Sustained eradication ^c	A urine culture taken at the TOC visit still shows eradication of the uropathogen (e.g., $\geq 10^5$ CFU/mL is reduced to $< 10^4$ CFU/mL) found at study entry.
Persistence	A urine culture taken at the TOC visit grows a uropathogen (at $\geq 10^4$ CFU/mL) found at study entry.
New Infection	A uropathogen, other than a microorganism found at baseline is present in the urine (at a level $\geq 10^5$ CFU/mL) any time after IV study therapy is finished; OR A pathogen is isolated from a distant (non-urine), sterile after IV study therapy has been completed.

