- Subject has an infection which should be managed by Staged Abdominal Repair (STAR) or open abdomen technique.
- Infections limited to the hollow viscus, such as simple cholecystitis and simple appendicitis, ischemic bowel disease without perforation, acute suppurative cholangitis and acute necrotizing pancreatitis

7. has a history of serious allergy, hypersensitivity (e.g., anaphylaxis), or any serious reaction to any of the following:

- Any carbapenem, cephalosporin, penicillin, or other β -lactam agent
- other β -lactamase inhibitors (e.g., tazobactam, sulbactam, clavulanic acid, avibactam)

8. is a female who is pregnant or is expecting to conceive (or is a male partner of a female who is expecting to conceive), is breastfeeding, or plans to breastfeed prior to completion of the study.

9. has a history of a seizure disorder (requiring ongoing treatment with anti-convulsive therapy or prior treatment with anti-convulsive therapy within the last 3 years).

10. is anticipated to be treated with any of the following medications during the course of study therapy:

- valproic acid (or has used valproic acid in the 2 weeks prior to screening)
- concomitant IV or oral antimicrobial treatments which is considered effective to the index pathogen, in addition to the study treatments.

NOTE: Use of IV vancomycin, IV daptomycin, or IV linezolid to treat confirmed or suspected methicillin-resistant *S. aureus* (MRSA) infection or use of IV linezolid to treat confirmed or suspected vancomycin-resistant *Enterococcus spp.* (VRE) infection is allowed. (Refer to Section 5.5).

11. is currently receiving immunosuppressive therapy, including use of high-dose corticosteroids (i.e., \geq 40 mg prednisone or prednisone equivalent per day).

NOTE: Prior short term use (\leq 7 days) of steroid therapy in the 30 days prior to study entry is allowed.

12. has an estimated or actual creatinine clearance of less than 15 mL/min at screening based on the findings of local laboratory values. Creatinine clearance in mL/min may be calculated from serum creatinine concentration by the C-G equation:

$$\text{Creatinine clearance (Males)} = \frac{\text{weight in kg} \times (140 \text{ minus age})}{(72) \times (\text{creatinine in mg/dL})}$$

Creatinine clearance (Females) = 0.85 \times the value obtained using the formula above

13. is currently undergoing hemodialysis or peritoneal dialysis.

14. has any of the following laboratory abnormalities at the time of screening:

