5.5 Concomitant Medications/Vaccinations (Allowed & Prohibited)

Medications or vaccinations specifically prohibited in the exclusion criteria are not allowed during the ongoing trial. If there is a clinical indication for any medication or vaccination specifically prohibited during the trial, discontinuation from trial therapy or vaccination may be required. The investigator should discuss any questions regarding this with the Sponsor Clinical Director. The final decision on any supportive therapy or vaccination rests with the investigator and/or the subject's primary physician. However, the decision to continue the subject on trial therapy or vaccination schedule requires the mutual agreement of the investigator, the Sponsor and the subject.

The following concomitant medications/therapies are not permitted in this study:

1. Valproic acid (during treatment with study drug and the 2 weeks prior to screening)
2. Non-study systemic (IV or oral) antibacterial treatments

NOTE: Use of IV vancomycin, IV daptomycin, or IV linezolid to treat confirmed or suspected methicillin-resistant *S. aureus* (MRSA) infection or use of IV linezolid to treat confirmed or suspected vancomycin-resistant *Enterococcus* spp. (VRE) infection is allowed.

3. Systemic (IV or oral) antifungal therapy

NOTE: Concomitant use of antifungal therapy for treatment of mucocutaneous infections (e.g., vaginal candidiasis, onychomycosis) is allowed.

4. Immunosuppressive therapy, including use of high-dose corticosteroids (i.e., ≥ 40 mg prednisone or prednisone equivalent per day)

NOTE: Short-term use (≤ 7 days) of systemic (Oral or IV) steroid therapy and Topical steroids for the treatment of skin conditions are also allowed.

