8.5.2 Efficacy Analysis Population

Two populations, the MITT and the ME populations, will be used for the analysis of efficacy data in this study. The ME population will serve as the primary population for efficacy analyses in this study.

The MITT population is defined as all enrolled subjects who receive at least one dose of IV study therapy. In this study, this is identical with the ASaT population. The ME population is a subset of the MITT population that excludes subjects due to major deviations from the protocol that may substantially affect the results of the efficacy analyses. Potential deviations that may result in the exclusion of a subject from the ME population include the following:

1. The subject fails to meet the protocol definition of cIAI or cUTI
2. The subject had significant violations of inclusion/exclusion criteria that could impact the efficacy assessment (e.g., receipt of previous or concurrent systemic antibacterial therapy beyond those allowed per protocol)
3. The subject received less than 96 hours of IV study therapy (16 infusions)
4. (cIAI only) The subject's pre-study/post-operative culture from the site of infection fails to grow at least 1 gram-negative enteric(s) and/or anaerobic pathogen(s) commonly isolated in IAI. (Note: Subjects who fail to grow a single gram-negative enteric and/or anaerobic pathogen from the site of infection are excluded from the ME population. That is, subjects with only gram-positive pathogens identified will be excluded, as well as those who do not grow any pathogens.)

(cUTI only) The subject's pre-study urine culture fails to grow at least 1 gram-negative and/or anaerobic, pathogen at sufficient quantity specified in the inclusion criteria (See Section 5.1.2 for details)

The composition of the ME population at each time point of interest will be made prior to the database lock and will be documented in a separate memo.

Details on the approach to handling missing data are provided in Section 8.6.

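### At TOC, an oral antibacterial given after IMI/REL does not stop a subject from being rated favorable, although Section 5.5 does not permit it

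*Combined protocol and SAP*

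**What the plan says.** **Endpoint definitions.** In Section 4.2.3.2.1.1, Cure at TOC (Table 3) requires resolution of signs and symptoms and that "no additional IV antibiotic therapy is required". Cure and Improved at EOT (Table 2) and the sepsis ratings (Tables 8 and 9) have the same IV-only condition. For cUTI, Table 7 defines sustained eradication by culture: "A urine culture taken at the TOC visit still shows eradication of the uropathogen". Its footnote c adds that the EOT rating must also have been eradication.

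**Concomitant therapy.** Section 5.5 opens its list with "The following concomitant medications/therapies are not permitted in this study", and item 2 is "Non-study systemic (IV or oral) antibacterial treatments". That item has no end date. Its stated exceptions are IV agents for MRSA or VRE.

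**Analysis rules.** Section 8.5.2 item 2 gives, as an example of a violation that could affect efficacy, "receipt of previous or concurrent systemic antibacterial therapy beyond those allowed per protocol". The list is introduced by "Potential deviations that may result in the exclusion of a subject from the ME population include the following". Section 8.6.2, exception 2, imputes failure and persistence to subjects who discontinue IV therapy for lack of efficacy, explained as "withdrawals with subsequent non-study antibiotic therapy, subjects requiring therapy beyond 14 days". In MITT, only missing or indeterminate responses become failures.

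**Timing.** EOT is within 24 hours of the last IV dose (Section 7.1.5.2). TOC is 5 to 9 days after completion (Section 7.1.5.3).

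**The concern.** The secondary objectives (Section 3.2) estimate response to IMI/REL at TOC. If an oral antibacterial is taken between the last dose and TOC, the TOC rating reflects IMI/REL plus the later drug. The protocol bars that drug but gives it no consequence for the endpoint.

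There is no comparator in which the same practice would also appear. Both the primary (ME) and the supportive (MITT) rows of Table 18 use the same ratings, so comparing the two need not reveal the problem. The trial is open-label and the investigator makes the clinical rating. How these subjects are handled should therefore be fixed in advance rather than decided case by case.

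**Working it through.** **Step 1. Apply each rule to one subject.** The subject completes IMI/REL within 14 days, then takes an oral antibacterial for the index infection before TOC. At TOC the signs have resolved, or the urine culture is negative.

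| Rule | Effect on this subject |
|---|---|
| 5.5 item 2 | Not permitted, but no response rating follows |
| 5.1.3 criterion 10 | Silent: it concerns a subject who "is anticipated to be treated with any of the following medications during the course of study therapy", not the interval after therapy |
| Tables 3 and 9, Cure | Condition met, since the drug is oral |
| Table 7, sustained eradication | Met if EOT was eradication and the TOC culture is negative |
| 8.5.2 item 2 | Names earlier or concurrent therapy, not later therapy; removal is discretionary |
| 8.6.2 exception 2 | Not met: no discontinuation for lack of efficacy, and no need for therapy past day 14 |
| MITT rule | Not met: the response is neither missing nor indeterminate |
| Indeterminate categories (Tables 3 and 7) | Could be used, but only by judgment |

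The 14-day wording leaves room for this case. If the last dose is on day 5, TOC falls on day 5 + 5 = 10 to day 5 + 9 = 14. An oral course covering the whole interval to TOC need not run past day 14.

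**Step 2. Which endpoints are exposed.**
- cIAI clinical response at TOC (secondary): exposed. Improved at EOT can become Cure at TOC while on the oral drug.
- cUTI microbiological response at TOC (secondary): exposed in one way only. Footnote c requires eradication at EOT, so the oral drug cannot turn an EOT non-eradicator into a success. It can suppress a recurrence.
- Sepsis composite at TOC (exploratory, described per subject): the same clinical wording applies.
- Primary EOT endpoints: see the objection.

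**Step 3. Scale.** Inputs from Section 8.9 and Table 19: 28 evaluable ME subjects, 26 favorable, 95% Agresti-Coull interval. This is the plan's EOT scenario, borrowed here only to show scale at TOC.

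With z = 1.96: n~ = n + z², p~ = (x + z²/2)/n~, interval = p~ ± z√(p~(1 − p~)/n~), cut at 100%.

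Reproducing the plan: n~ = 28 + 3.84 = 31.84; p~ = (26 + 1.92)/31.84 = 0.877; half-width = 1.96 × √(0.877 × 0.123/31.84) = 0.114. The result is 92.9% (76.3, 99.1), as stated. All eight rows of Table 19 reproduce.

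Now assume that k of the 26 favorable subjects took such an oral drug before TOC. The k values are assumptions.

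| k | Left favorable | Counted unfavorable | Dropped from ME |
|---|---|---|---|
| 1 | 92.9 (76.3, 99.1) | 25/28 = 89.3 (72.0, 97.1) | 25/27 = 92.6 (75.5, 99.0) |
| 2 | 92.9 (76.3, 99.1) | 24/28 = 85.7 (67.9, 94.9) | 24/26 = 92.3 (74.7, 99.0) |
| 3 | 92.9 (76.3, 99.1) | 23/28 = 82.1 (63.9, 92.6) | 23/25 = 92.0 (73.9, 98.9) |
| 5 | 92.9 (76.3, 99.1) | 21/28 = 75.0 (56.4, 87.6) | 21/23 = 91.3 (72.0, 98.8) |

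Each reclassified subject moves the ME estimate by 1/28 = 3.6 points. In a MITT cohort of 40 it is 1/40 = 2.5 points. Dropping subjects from ME gives almost the same estimate as leaving them favorable.

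**The case against.** A reader might infer that the primary EOT results also credit IMI/REL with another drug's effect. The documents do not support that. EOT falls within 24 hours of the last IV dose, so a drug started after completion has little or no time to act. The cUTI primary endpoint is the EOT urine culture, which does not use the Cure or Improved wording. For cIAI, Improved allows residual signs by design. What remains at EOT is narrower: an Improved cIAI subject judged to need further oral therapy is still favorable.

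A reader might also infer that the plan permits oral follow-on treatment, or that such a subject is certain to count as a success in MITT. Neither follows. Section 5.5 does not permit it. Because it is a deviation, the rating could be set to Indeterminate: Table 3 allows this for extenuating circumstances, and Table 7 for a protocol violation that prevents assessment. Indeterminate is a failure in MITT and an exclusion in ME. Section 8.5.2 also lets ME membership be settled for each time point before database lock, and a subject who needs treatment past day 14 may be caught by exception 2.

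These points stand and limit the claim. They do not close the gap. Each is discretionary or reaches only part of the group, and the same subject could end up favorable, failed or excluded.

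Two further objections are fair. The 26/28 scenario is for EOT and the counts are assumed. Imposing persistence on a subject stopped for an adverse event, against a negative culture, would replace data with an imputation unrelated to inefficacy.

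**Conclusion.** The point holds for TOC. The endpoint wording and Section 5.5 do not agree, and no rule rates a subject who completes IMI/REL within 14 days and then takes an oral antibacterial for the index infection before TOC. On the literal text that subject can be favorable in ME and MITT, so both secondary estimates can be biased upward. For cUTI the route is limited to masked recurrence.

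The size cannot be derived, because the documents give no rate of such use. On the assumption of 28 evaluable subjects, each one is worth 3.6 points. With five, the choice of rule alone separates 92.9%, 91.3% and 75.0%. This is a single-arm estimation trial with no success threshold, so the effect is on the interpretation of the TOC estimates and not on a test. Whether oral follow-on treatment ought to be allowed is a clinical matter and is not judged here.

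**What to change.** 1. Reconcile Tables 3 and 9 with Section 5.5: replace the IV-only condition with one covering systemic antibacterial therapy, IV or oral, for the index infection.
2. Add to Section 8.6.2: a subject who receives such non-study therapy after IMI/REL and before TOC is not counted as favorable at TOC, in ME or in MITT, and is not dropped from ME for that reason. Exempt agents that Section 5.5 allows and treatment of unrelated infections.
3. Report a TOC sensitivity analysis with these subjects rated as observed. Handle subjects stopped for an adverse event with a negative culture in that analysis, not by imposed persistence.
4. Report by cohort how many subjects received such therapy before TOC.

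The cost is wording in two tables, one analysis rule and one extra analysis. Concomitant medication is already reviewed at every visit through follow-up (Section 6.0). Analysis changes before database lock can go in the supplemental SAP (Section 8.0). The downside is that reported TOC rates may be slightly lower.
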